****VUMC ONLY:** Due to the unprecedeted situation surrounding the global COVID-19 pandemic, we will, via email, ask currently-enrolled families (only at the VUMC site) from Cohort 4 and 5 (and all future subjects) to complete the following three questionnaires, which relate to stress and coping associated with COVID-19, via REDCap online survey or, if they choose, using physical copies of the questionnaires that we would mail to them:

VUMC ONLY: 1) Compas Responses to Stress Questionnaire (RSQ; Compas, 2020) - COVID-19 Child Self-Report: The RSQ can be filled out by children and adolescents regarding their own personal coping and involuntary stress responses in regards to how they respond to stress related to COVID-19.

VUMC ONLY: 2) Compas Responses to Stress Questionnaire (RSQ; Compas, 2020) - COVID-19 Adult Self-Report: The RSQ can be filled out by parents regarding their own personal coping and involuntary stress responses in regards to how they respond to stress related to COVID-19.

VUMC ONLY: 3) Compas Responses to Stress Questionnaire (RSQ; Compas, 2020) - COVID-19 Parent Report on Child: The RSQ can be filled out by parents regarding their child's coping and involuntary stress responses in regards to how their child responds to stress related to COVID-19.

ASSESSMENT VISIT

SETUP & CONSENTING

- Arrive at the assessment facilities 30 minutes prior to family arrival time.
- Gather appropriate testing materials out of cabinets (ADOS, NEPSY, WASI)
- When the family arrives bring them into a private family room and begin consenting. (15 minutes)
 - Ensure that 2 consent & 2 assent forms are signed by the family and research staff (1 copy for research team & 1 for family)
 - Take the **child's photo** (after parent or guardian has signed Video/Photo Release). Explain that picture will be used during counselor/peer matching.
 - Explain **NDAR** (National Database for Autism Research), and also explain GUID and need for **child's city of birth** in creating unique identifier (see page 14).
- Leave the parent in the family room where they'll wait until the assessment is done with child
 - Retrieve any filled surveys that will be scored later, make sure to check that all files have been answered entirely
- Consenting for Peer Control Group:

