***Follow-Up forms sent to both Experimental and Control groups approximately 8 weeks after post-visits.**

FOLLOW- UP ERP

- Protocol for ERP does not change in follow-up visit.
- ERP may come before Assessment during follow-up

FOLLOW- UP CASS

- Utilize research helpers unknown to participant (not the same research helpers as in the pre and post- CASS)

SENSE THEATRE/TACKLING TEENAGE TRAINING INTERVENTION PREPARATION

GROUP ASSIGNMENT

- Once randomization into SENSE Theatre or TTT is complete and participants have been assigned to groups, send letters to families informing them of what group they are assigned.
- Send out RedCap survey which collects information regarding Medication (see if there have been any changes), food allergies, behavioral information, t-shirt size.
- Add participant and research helper contacts to a designated lab cell phone

PEERS/COUNSELORS

- **Application:** Interested peers and counselors will complete an application
- **Decisions:** Lead site investigator, and theatre director will narrow down who is to be interviewed for a peer and counselor position.
- **Background checks:** all adults participating in the intervention (18 years +) must have an existing background check with Vanderbilt or go through the process of getting one.
- **Protection of Minors Training:** Make sure all counselors and peers are compliant with the site's requirements for protections of minors training. Contact site IRB for "Research Involving Minors" for more information pertinent to site requirements.
- **Consent and Video Release Forms:** sent to peers/counselors participating in intervention.
- **Intervention Information:** Send training schedule, location map, and first days schedule (via email), and an email reminder 1 week before training begins.

TRAINING

SPEAKERS

- Site PI will be responsible for contacting and choosing speakers.
- Coordinate who will be presenting when, 6 weeks before intervention begins.
 - Research Assistant/Coordinator—"Introduction to Autism"
 - Confidentiality & Code of Conduct, SENSE Theatre Manual, SENSE Lab & Theatre, Behavioral Strategies.
- Copies of past presentations can be provided to any sites by the SENSE Research Coordinator.

BINDERS

- Binder Materials:
 - Binder Covers (Color)
 - Binder spine labels (color)

- Divider Tab Labels
- Presentations (Black and White)
- Schedule
- Music/Lyrics (SENSE Theatre Intervention only)
- Name Tags
- Pre/Post Test
- SENSE Theatre Manual (Black and White)

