Investigating Social Competence in Youth with Autism: A Multisite
RCT

Statistical Analysis Plan (SAP)

NCT03368001

Document Date: November 1, 2017

Document Source: Analytic Plan from MH114906

3.C.12. ANALYTIC PLAN: Aims and Hypotheses (Hyp)

Handling missing data, Full information maximum likelihood (FIML) estimation methods will be used.

Specific Aim 1: Show Efficacy of SENSE via Target Engagement of Memory for Faces

Hyp 1.1: Youth in the EXP group will demonstrate significantly faster growth in memory for faces (MFD and IMF) than youth in the ACC group. EXP youth will also have higher levels of memory for faces at follow-up.

Hyp 2.1: Youth in the EXP group will demonstrate significantly faster growth in social behavior (SRS and CASS) than youth in the ACC group. EXP youth will also have higher levels of prosocial behavior at follow-up.

Statistical Analysis: To address the above-mentioned hypothesis, we will use a 2-level multilevel growth model with treatment (EXP vs. ACC) predicting random intercepts and random linear slopes. The levels are (1) time of testing in months from study entry and (2) participant. Time will be centered at follow-up to enable interpreting the intercept as an end-point estimate. We will test EXP vs. ACC differences on means of the linear slope of time in order to test for differential change over time. We will also test EXP vs. ACC differences in follow-up-centered intercepts. A linear model is a reasonable model of social growth for such a short period (i.e., three months) with people who have a social impairment. The random intercept and slope accommodate dependency of time (pre, post, follow-up) within participant. Dependency of participants within cohort will be corrected for using design-robust standard errors (following procedures in Sterba¹²⁶). Site effects are not anticipated but will be examined by including 2 dummy covariates for site as predictors of intercepts and slopes; if not significant, these covariates will be removed. This model will be run in Mplus¹²⁷ general multilevel and structural equation modeling software capable of fitting both the univariate multilevel models for Specific Aim 1 and the multivariate multilevel models for Specific Aim 2, below.

Specific Aim 2: Linking Degree of Target Engagement and Mechanism-Based Functional Outcomes

Hyp 2.2. Growth in memory for faces (NEPSY, ERP) will mediate the effect of treatment on growth in social behavior (SRS, CASS).

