Statistical Analysis: To address Hyp 2.2, we will use a multivariate multilevel growth model (involving a linear growth model for memory and another linear growth model for social behavior). We will specify a mediation pathway at the participant-level from treatment (x) to the slope of memory for faces (m) to the slope of social behavior (y). The indirect effect will be tested using the 95% confidence interval around the product of the unstandardized coefficients for the (x→m) and (m→y) paths of the multilevel mediation model following procedures of Lachowicz, Sterba, and Preacher¹²⁸. The confidence interval will be estimated using the Monte-Carlo procedure described in Preacher and Selig,¹²⁹. Exclusion of zero will be interpreted as a significant indirect effect.

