Power Using Attrition-adjusted Sample Size: Because missing data will be handled using FIML, the only dropouts will be those with no data (they were randomized but did not show up for any assessment). Past SENSE Theatre studies, including the previous RCT, had less than 10% post-Time 1 attrition. Virginia Tech, in unrelated, recent intervention RCTs had <17% attrition (teens) and 0% (adults); Stony Brook has had 0% attrition in recent RCTs of teens and adults. Thus, to plan conservatively, we will plan for a 90% retention rate. Power analyses were conducted using a proposed sample size that is adjusted for a 10% attrition rate, which is quite feasible. The probability of detecting a treatment effect and the effect size of between-group differences are understandably lower for dependent variables derived from far transfer procedures and for distal variables. The primary dependent variable (memory for faces) and the behavioral measure of social behavior (CASS variable) represent such outcomes. While the estimation of effect sizes from small pilot studies may be limited due to sampling variability¹³⁰, an established literature of theatre-based interventions does not exist. Using past meta-analyses of such outcomes and professional discussion about such effect sizes, clinically important outcomes for treatment-control differences in slopes are those exceeding Cohen's *d* of .25^{131,132}. The guidelines for effect sizes of indirect effects call indirect effects (i.e., product of the standardized coefficients for the x→m and m→y paths) greater than .10 'medium' effect sizes, and such effects are judged to be clinically important¹³³. Regarding Specific Aim 1, we anticipate a Cohen's *d* of at least .5 for the efficacy tests. Regarding Specific Aim 2, based on the past mediation analysis, we expect an indirect effect of at least .23. To demonstrate that our proposed sample size is more than adequate to detect even lower-than-expected effect sizes, we compute the minimally-acceptable effect size for 80% power with 216 participants. For the 2-level multilevel models used in investigating Specific Aim 1, with 216 participants, we will have 82% power for a Cohen's *d* as low as .2 with an ICC for within-participant dependence of .1. For Aim 2, involving mediation effects, we'll need a product of the x→m and m→y standardized coefficients of at least .056 with 216 participants using the confidence interval around the indirect effect to test significance¹³³. There will be plenty of power with the proposed sample size to detect the predicted effect sizes.

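### Cohort dependence is handled by robust standard errors, but the SAP text fixes neither the cohort, nor the number of cohorts, nor a small-sample reference; with a normal cutoff the 5% tests could run at about 6-8%, or 9-15% if cohorts are few

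*SAP*

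**What the plan says.** The SAP's Statistical Analysis for Hyp 1.1 and 2.1 fits a growth model with two levels, time and participant. It tests the arm difference in the slope and in the level at follow-up. Cohort is not a level of the model. It enters through one sentence, "Dependency of participants within cohort will be corrected for using design-robust standard errors", which refers to a cited procedure and is followed by the choice of Mplus as software.

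The other places that bear on the point:

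- **Sites.** The same paragraph speaks of "including 2 dummy covariates for site as predictors of intercepts and slopes", which implies three sites.
- **Cohort count.** Neither document gives one. The only clue is in the Protocol under Visit 1 (Pre-Test) Only, where COVID-19 questionnaires at one site go to families "from Cohort 4 and 5 (and all future subjects". Labels therefore reached at least 5 at that site, with more children expected.
- **Arms and cohorts.** The Protocol's Group Assignment section begins "Once randomization into SENSE Theatre or TTT is complete and participants have been assigned to groups". Neither document says whether each cohort contains both arms.
- **Hyp 2.2.** "The confidence interval will be estimated using the Monte-Carlo procedure". That paragraph does not mention cohort.
- **Power.** The SAP states that "with 216 participants, we will have 82% power" at d = .2, with an ICC for dependence within participant of .1. It gives no cohort ICC.

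**The concern.** A cluster-robust standard error is estimated from variation between clusters. Its precision depends on the number of cohorts, not on the 216 children. With few cohorts it is biased downward and noisy, and a normal cutoff of 1.96 is then too lenient. This happens even if cohorts have no true effect, because the problem lies in estimating a variance from few units.

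The robust standard error is the only protection against cohort dependence that the SAP states, and it feeds every treatment test under Hyp 1.1 and 2.1. Which correction is right depends on what a cohort is and whether it holds both arms. If that is settled after the data are seen, a borderline result could turn on the choice.

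**Working it through.** **The plan's own figure.** The SAP gives no type I error. Its only operating figure for Aim 1 is 82% power, which I use below as given. I could not reproduce it. With 108 per arm (1:1 assumed) and ICC .1, the mean of three measures has variance (1 + 2 x .1)/3 = .40, and the slope per wave has (1 - .1)/2 = .45. Then d/SE = .2/sqrt(2 x .40/108) = 2.32 and .2/sqrt(2 x .45/108) = 2.19. Power is 64% and 59% two-sided, or 75% and 71% one-sided. The slope SD, time scale, level and sidedness are not stated, so I do not call the 82% wrong. It does not bear on this point.

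**Inputs**

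- N = 216 (SAP, power section); three sites (two dummies).
- Assumed: 1:1 allocation; two-sided 5%, in line with the 95% interval for Hyp 2.2 (no level is stated for Hyp 1.1/2.1); a normal cutoff.
- Assumed G: 5-8 cohorts per label series. The 5 is a floor from the Protocol; the 8 is my assumption. This gives G = 5-8 if cohorts are study-wide waves and 3 x 5 to 3 x 8 = 15-24 if they are site-specific.

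**Both arms in each cohort, equal sizes.** The treatment effect is the mean of G within-cohort differences, and the uncorrected robust variance is (G-1)/G times the usual one. Hence:

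- without a finite-cluster factor: 2P(T with G-1 df > 1.96 sqrt((G-1)/G));
- with the G/(G-1) factor: 2P(T with G-1 df > 1.96).

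At G = 15 the first cutoff is 1.96 x sqrt(14/15) = 1.894, which gives 7.9%; with the factor it is 7.0%.

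| G | Without factor | With factor |
|---|---|---|
| 5 | 15.4% | 12.2% |
| 8 | 10.9% | 9.1% |
| 15 | 7.9% | 7.0% |
| 24 | 6.8% | 6.2% |

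A simulation with one score per child standing in for the slope or follow-up level agrees (4,000 runs): 16.3/12.4%, 11.5/9.7%, 8.0/6.9% and 7.2/6.7%.

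**Unequal cohorts.** With a 4-fold range of sizes and an assumed cohort-by-arm ICC of .05, simulation gives 17.8/14.4% (G = 5), 12.4/10.5% (8), 8.4/7.5% (15) and 7.1/6.6% (24). With ICC 0 the uncorrected error is still 16.6% at G = 5 and 8.5% at G = 15.

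**Single-arm clusters.** With G counting all clusters, the error is 2P(T with G-2 df > 1.96 sqrt((G-2)/G)) without a factor. With the G/(G-1) factor, (G-2)/G becomes (G-2)/(G-1). Results: 11.8/10.2% at 10 clusters, 8.8/7.9% at 16, 6.9/6.4% at 30 and 6.1/5.9% at 48.

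**Does the remedy work?** With both arms in each cohort, the G/(G-1) factor and t with G-1 df give 4.7-5.0% for equal cohorts. With a 4-fold range they give 6.4% (G = 5), 6.0% (8), 5.3% (15) and 5.3% (24). CR2 with Satterthwaite df holds 4.3-5.3% in the unequal both-arm cases. If the printed standard error already contains the factor and it is applied again, the test becomes conservative: 3.6% (G = 5), 3.9% (8) and 4.3% (15).

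**Price of the remedy, both arms in each cohort.** The interval width ratio is t(.975, G-1)/1.96 if the factor is already in the standard error, and that times sqrt(G/(G-1)) if not: 1.42-1.58 (G = 5), 1.21-1.29 (8), 1.09-1.13 (15) and 1.05-1.08 (24). Power, from a noncentral t with noncentrality 1.960 + 0.915 = 2.875 (82% with a normal cutoff), is 58%, 69.5%, 76% and 79%.

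**Hyp 2.2, if the same uncorrected standard errors feed the interval.** With no treatment-to-memory path and a memory-to-behaviour path of .4-.5, simulated false positives are about 13-16% (G = 5), 9-11% (8) and 6-9% (15-24). With both paths zero they stay below 2.5%.

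**The case against.** The method is not left blank. The SAP defers to a cited procedure that may contain a small-sample correction, and the document is an excerpt from a grant's analytic plan, so a cohort definition could stand elsewhere. What is shown is an omission in the text supplied. This stands, and it makes every error rate above conditional.

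The inputs are assumed. The Protocol's cohort labels come from COVID-era text and cannot show the G planned in a SAP dated November 2017. With 30 cohorts the closed form gives only 6.0-6.4%. This also stands. But a citation to a general procedure does not by itself fix this trial's clusters or G.

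The effect is modest in what I take to be the likelier, site-specific case. Agreed; the point is a worthwhile improvement, not a fatal fault.

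The single-arm reading has weak support, because the SAP uses cohort for the unit of dependence and group for the arm. That is fair. It matters only because the documents do not exclude it and it changes the degrees of freedom.

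A reader might infer that the primary tests do run at up to 15%, or that clustering is ignored. The documents support neither: cohort is named and a correction is planned, and the cutoff and G are unknown. Nor do they show that the Hyp 2.2 interval is too narrow. That is an inference, since its paragraph does not mention cohort.

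**Conclusion.** The point holds in conditional form. Cohort is named but not defined, and the SAP text gives no G, small-sample correction or reference distribution. If robust standard errors are used with a normal cutoff, a two-sided 5% test runs at about 6-8% with 15-24 equal site-specific cohorts and about 9-15% with 5-8 study-wide waves. Unequal sizes push these up, and 10-16 single-arm clusters would give about 8-12%, so few study-wide waves are not the only route to a larger error.

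The result rests on assumed G, level, allocation and cutoff, and on a one-score stand-in for the growth model; the unequal-size and mediation figures also rest on an assumed ICC. Confidence is medium. The change should be made, because it is cheap and settles a choice that affects all the Hyp 1.1 and 2.1 treatment tests.

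**What to change.** Before analysis, add a few lines to the SAP:

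1. Define the cohort (site-specific cohort, study-wide wave or single-arm intervention group), say whether both arms are in each, and state G.
2. For each Hyp 1.1 and 2.1 treatment test, replace any normal cutoff with t on G-1 df, or G-2 df if clusters are single-arm.
3. Check whether the printed standard error or the cited procedure already includes a finite-cluster factor. Only if neither does, multiply by sqrt(G/(G-1)), or sqrt(G/(G-2)) for single-arm clusters.
4. If cohort sizes are clearly unequal, use CR2 with Satterthwaite df where the software allows.
5. For Hyp 2.2, state whether cohort-robust standard errors enter the Monte Carlo interval and, if so, use the corrected ones.

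Items 2 and 3 need only arithmetic on printed output; CR2 needs a re-fit. With both arms in each cohort, intervals widen by about 5-13% at 15-24 cohorts, 21-29% at 8 and 42-58% at 5; the lower end of each range applies if the factor is already in the standard error. At 15-24 cohorts the loss is about 3-6 points of the stated 82% power. It is larger with fewer cohorts, down to 58% power at G = 5.

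### Site enters the growth models only as arm-common terms that are dropped if not significant, and no by-site view of the treatment effect is planned

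*SAP*

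**What the plan says.** The SAP (3.C.12, Statistical Analysis for Hyp 1.1 and 2.1) specifies a "2-level multilevel growth model with treatment (EXP vs. ACC) predicting random intercepts and random linear slopes". It estimates one EXP versus ACC difference in slope and one in the intercept centred at follow-up.

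Site is dealt with in one sentence, which opens: "Site effects are not anticipated but will be examined by including 2 dummy covariates for site as predictors of intercepts and slopes". The same sentence closes with a removal rule: "if not significant, these covariates will be removed". Two dummies imply three sites. The SAP does not state the significance level, whether the dummies are tested jointly or one by one, or whether the decision is taken once or separately for each outcome.

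Clustering is addressed for cohort only: "Dependency of participants within cohort will be corrected for using design-robust standard errors". That changes the standard error; it does not describe how the effect varies by site.

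Neither document contains a treatment-by-site term, a site-specific treatment estimate or any other heterogeneity analysis. The Aim 2 mediation model does not mention site.

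**The concern.** Two things look wrong, and they should be kept apart.

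- **The model is chosen by the data.** Non-significance is treated as absence of a site effect. With several outcomes (two memory-for-faces measures, SRS, CASS) and no stated test rule, one outcome may be analysed with site and another without.
- **The treatment effect cannot vary by site in any planned analysis.** The dummies shift the average intercept and slope of both arms together. Whether they are kept or dropped says nothing about whether EXP beats ACC at each site.

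Some variation in delivery is plausible. Under Training, Speakers, the Protocol says "Site PI will be responsible for contacting and choosing speakers", and under Peers/Counselors the lead site investigator and theatre director narrow down whom to interview. At stake is how far the pooled result of a multisite trial can be read as consistent across its sites.

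**Working it through.** **Inputs from the SAP.** Two site dummies, hence three sites; 216 participants; clinically important slope difference d above .25; anticipated d of at least .5.

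**Assumptions, not in the documents.** 72 per site (216/3), 1:1 allocation within site (36 per arm), two-sided .05, and slopes treated as one standardised outcome with SD 1 and no measurement error.

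**The plan's own figure.** The SAP gives no figure for the site check. Its nearest statement is "with 216 participants, we will have 82% power for a Cohen's *d* as low as .2 with an ICC for within-participant dependence of .1". Simple two-arm approximations at two-sided .05 give 64% (mean of three occasions) or 59% (slope of .2 per occasion), so it was not reproduced. Nothing below depends on it.

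**1. How often the site terms are removed.** Suppose one site differs by δ from the other two. The noncentrality is λ = 72 × Σ(mⱼ − m̄)² = 72 × (2/3)δ² = 48δ², and removal is the probability that a noncentral F(2, 212) falls below its 5% critical value.

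| δ (SD) | λ | removed |
|---|---|---|
| 0 | 0 | 95% |
| .1 | 0.48 | 91% |
| .2 | 1.92 | 78% |
| .3 | 4.32 | 56% |
| .4 | 7.68 | 31% |
| .5 | 12.0 | 12% |

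The SAP does not say that this is the test. If any one of the four coefficients (two on intercept, two on slope) at unadjusted .05 is enough for retention, removal is rarer. By simulation it is about 20-40% at δ = .3, with the same standardised difference on the intercept, an intercept-slope correlation of .3 to .7, and either choice of reference site. Under that rule with no true site effect, at least one coefficient is significant in about 1 − .95⁴ = 19% of trials (independence approximation).

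**2. What removal costs.** With balanced arms, dropping a difference δ at one of three equal sites adds δ² × (1/3) × (2/3) = 2δ²/9 to the residual variance.

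- δ = .3: .02, and √1.02 = 1.010, about 1% on the standard error.
- δ = .5: .056, and √1.056 = 1.027, about 2.7%.

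If the realised allocation differs between sites, dropping site also shifts the treatment difference by δ × (EXP share at that site − ACC share at that site). With δ = .5 and an illustrative gap of .10 in shares, that is .05 SD.

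**3. What the site terms can show about the treatment effect.** Take slope effects of d = .5, .2 and .2 with equal control means.

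- Pooled effect: (.5 + .2 + .2)/3 = .30, above .25, while two sites lie below .25.
- Averaged over arms, the site means are .25, .10 and .10, so only half of the gap is visible: λ = 72 × (.10² + .05² + .05²) = 1.08. The 2-df test removes site in 86% of trials (about 61-73% under the any-coefficient rule).

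A 20,000-replicate simulation of the 2-df test shows that retention does not track heterogeneity:

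- d = .5 at one site and 0 at the others, equal control means: site kept in 31%.
- The same effects, with that site's control mean .25 lower, so that its average over arms is −.25 + .25 = 0: kept in 5%.
- Equal effects everywhere, with one site offset by .5 in both arms: kept in 88%.

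**4. What a by-site table could show.**

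- One site: SE = √(2/36) = .236; half-width 1.96 × .236 = .46 SD.
- Two sites pooled: SE = √(2/72) = .167; half-width .33 SD.
- One site against the other two: SE = √(4/72 + 4/144) = .289; 80% power needs a gap of (1.96 + .84) × .289 = .81. For .5 against 0, power is 41% on 1 df and 32% on 2 df.

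**The case against.** The strongest reply is that Hyp 1.1 and 2.1 are pooled EXP versus ACC contrasts. The SAP promises no site-specific efficacy, the cost of dropping site is small under balance, and a table with ±.46 SD per site can rarely separate a working site from a weak one. All of that stands. It makes this an improvement to the plan, not the repair of a faulty primary test.

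Four stronger readings are tempting, and the documents do not support them.

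- *The site terms will usually vanish.* That holds if site differences are nil, as the SAP expects, or no more than about .3 SD under the 2-df slope test. Differences of .4 to .5 SD are kept in about 69-88% of trials, and the any-coefficient rule keeps them more often.
- *Removal is what hides site-specific efficacy.* It is not. The missing treatment-by-site term does that, and would do so if the dummies were always kept.
- *The other sites are known to be less experienced in delivery.* The SAP's sentence "Past SENSE Theatre studies, including the previous RCT, had less than 10% post-Time 1 attrition" and those that follow it concern attrition. Only one other site's trials are described as unconnected with this work. Neither document names an originating site.
- *Delivery is left to each site.* Neither document says that sites choose their own directors. The Protocol's Training section also lists a common SENSE Theatre manual and past presentations that can be supplied to any site.

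**Conclusion.** The point holds as two modest, separate weaknesses. The final model rests on an incompletely specified significance test and may differ between outcomes. Separately, no planned analysis shows whether the treatment effect is consistent across sites, so a pooled d of .30 could stand above the SAP's threshold with two of three sites below it.

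The removal rates of 56%, 31% and 12% depend on the assumed 72 per site, two-sided .05 and a single 2-df slope test. Less reliable slopes would raise them; a rule retaining site on any single coefficient would lower them. A reader might infer that the primary treatment test is biased. With balanced arms within site it is not, and the precision cost is about 1-3%. A shift in the estimate arises only if the site mix differs between arms, and the documents do not say whether randomisation is balanced by site. This is a cheap improvement.

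**What to change.** 1. In the SAP, delete "if not significant, these covariates will be removed". State that the two site dummies stay as predictors of intercept and slope in every model and for every outcome, including both growth processes of the Aim 2 model, whatever their significance.
2. Pre-specify one descriptive table per outcome: the EXP versus ACC slope difference with its 95% confidence interval at each site, from a model with treatment-by-site terms. State that no decision rests on the interaction p-value.

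The cost is SAP wording, one table and a few degrees of freedom out of 216 participants. The by-site intervals will be wide, so the table is estimation only and cannot establish or exclude efficacy at any one site; the SAP should say so.

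### The single Aim 1 power figure (82% at d = .2) names no contrast; it cannot hold for the follow-up intercept test and cannot be reproduced for the slope test

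*SAP*

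**What the plan says.** The SAP's Aim 1 statistical analysis fits a two-level growth model to three assessments (pre, post, follow-up), with time in months and centred at follow-up. Treatment predicts a random intercept and a random linear slope. Two group differences are to be tested: the mean slope, and the intercept, which represents the level at follow-up. Hyp 1.1 has a sentence for each.

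The power section gives one figure for Aim 1: "For the 2-level multilevel models used in investigating Specific Aim 1, with 216 participants, we will have 82% power for a" given effect size. That effect size, expressed as Cohen's *d*, is then put "as low as .2 with an ICC for within-participant dependence of .1". The figure is introduced by "we compute the minimally-acceptable effect size for 80% power with 216 participants", and its stated purpose is to show that "our proposed sample size is more than adequate to detect even lower-than-expected effect sizes".

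The same section expects a *d* "of at least .5 for the efficacy tests". It sets a clinical threshold of .25 with the words "clinically important outcomes for treatment-control differences in slopes are those exceeding" that value. It closes: "There will be plenty of power with the proposed sample size to detect the predicted effect sizes".

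For Aim 1 it gives no alpha, sidedness, allocation ratio, slope variance, standardising SD or time unit for *d*.

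**The concern.** Two contrasts from one growth model have different standard errors, so one power figure cannot be assumed to serve both. The follow-up intercept is estimated at the edge of the time range, and its precision is close to that of a single-visit comparison. A *d* of .2 with 108 children per arm would not be expected to give 82% power there. The slope has a different difficulty: its standardised size depends on whether *d* is per month, per wave or over the whole period, and this is not stated.

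At stake is how a null result would be read. Memory for faces is the variable the SAP calls primary, and its level at follow-up is half of Hyp 1.1. If 82% is taken to apply, a non-significant follow-up difference suggests that an effect of .2 was probably absent; at 36% power it suggests little. For the slope, a reader cannot tell whether the SAP's own threshold of .25 is detectable.

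**Working it through.** **Inputs from the SAP.** 216 participants, taken as already net of attrition because the section says the sample size is adjusted for it; ICC .1; three waves; *d* = .2, with .25 and .5 for comparison.

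**Assumptions.** 1:1 allocation (108 per arm), two-sided .05, complete data, total variance 1 (between-child .1, residual .9), equally spaced waves, normal approximation, no cohort clustering.

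**The plan's figure.** The stated inputs do not determine 82% for either contrast, so each is computed in turn.

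**Follow-up intercept.** With treatment predicting both intercept and slope and balanced data, the per-child variance is

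.1 + .9 × (1/3 + 1/2) = .1 + .75 = .85

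The 1/2 is the squared distance of the last wave from the mean time, divided by the sum of squares (1²/2). Then

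SE = √(.85 × 2/108) = .1255

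| *d* | *d*/SE | power, two-sided | power, one-sided |
|---|---|---|---|
| .20 | 1.59 | 36% | 48% |
| .25 | 1.99 | 51% | 64% |
| .50 | 3.98 | 98% | 99% |

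- 80% power needs *d* = (1.960 + .842) × .1255 = .35 (one-sided .31).
- 82% at *d* = .2 needs a per-child variance of 54 × (.2/2.875)² = .261, against .85. Equivalently, N = 4 × .85 × (2.875/.2)², about 703.

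Sensitivity at *d* = .2:

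- *Visit timing.* The Protocol gives a 10-week programme (about 2.3 months), and follow-up 3 months after the post visit or follow-up forms about 8 weeks after it. Visits at 0, 2.3 and 5.3 months give 34.5%; at 0, 2.3 and 4.14 months, 37.0%. Both schedules are assumptions: they allow no gaps around treatment, and the second treats the form date as the visit date.
- *ICC from 0 to .9, equal spacing.* 36% down to 32%.
- *One-sided.* At most 50% over these ICCs and timings.
- *Another SD for d.* Residual SD 33%; between-child SD 8%.

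**Slope.** The per-child variance is .9/Sxx plus any random-slope variance, where Sxx is the sum of squared deviations of the visit times. With no slope variance, two-sided:

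| Meaning of *d* | Sxx | SE | slope difference at *d* = .2 | power at .2 | at .25 | at .5 |
|---|---|---|---|---|---|---|
| whole period, equal waves | 2 | .0913 | .1 per wave | 19% | 28% | 78% |
| per wave | 2 | .0913 | .2 per wave | 59% | 78% | >99% |
| per month, visits at 0, 1.5, 3 months | 4.5 | .0609 | .2 per month | 91% | 98% | >99% |

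The three-month span is the SAP's own description of the growth period. On the two longer schedules, per-month power at *d* = .2 exceeds 99%.

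Values near 82% can be reached by adding inputs:

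- *d* per month over three months with a random-slope SD of .248 per month: variance .2 + .248² = .2615, SE = √(.2615 × 2/108) = .0696, .2/.0696 = 2.87, power 82%.
- *d* as the pre-to-post difference, visits at 0, 2.3 and 5.3 months, one-sided: Sxx = 14.13, SE = .0343, (.2/2.3)/.0343 = 2.53, power 81% (72% two-sided).

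The SAP states neither set of inputs.

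**The case against.** The strongest reply is that the SAP never attaches 82% to the intercept test. The sentence speaks of the models and names no contrast. The section's only explanation of what an Aim 1 *d* measures, at the .25 threshold, concerns differences in slopes, and the slope is the first test in both the hypothesis and the analysis text. This stands. A reader might infer that the SAP claims 82% power for the follow-up difference; the text does not go that far. On the slope reading, however, the follow-up test has no stated power and the slope figure still lacks the definitions needed to check it.

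A reader might also infer that the slope figure is an arithmetic error. The documents do not support this: reasonable definitions give values on both sides of 82%, and some reach it.

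Nor do the figures show a trial underpowered for the effect it expects. At *d* = .5 the intercept test has about 98% power. The slope test exceeds 99% per wave or per month, and falls just short of 80%, at 78%, only if *d* is a whole-period difference. The closing claim, limited to the predicted effects, largely survives.

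Finally, the 36% rests on inputs the SAP does not state. That is true, but none of the alternatives tried takes the intercept test above about 50%.

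**Conclusion.** The point holds as one of attribution and missing definitions, with one firm numerical result: 82% power at *d* = .2 is not attainable for the follow-up intercept with 216 participants and an ICC of .1. Under the listed assumptions power is about 36% (34.5% to 37% on the other visit timings), and the adequacy claim for smaller effects reaches down to about *d* = .35, not .2. Positive clustering by cohort, which the analysis corrects for but the power section does not mention, would generally lower power further.

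For the slope, the figure is undetermined rather than wrong: 19% to over 99% at *d* = .2, depending mainly on the time unit. This should be corrected, but it does not threaten the design at the expected effect size.

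**What to change.** 1. Limit the 82% sentence to the slope contrast and give the definition behind it: time unit and SD of *d*, slope variance, alpha, sidedness, allocation and visit times. If that definition cannot be recovered, replace the figure with one recalculated on the sponsor's chosen scale.
2. Add a separate statement for the follow-up intercept, conditional on the sponsor's own inputs. For example: *Assuming two-sided .05, 1:1 allocation, 216 participants with three equally spaced complete waves, a within-participant ICC of .1 and d in total-SD units, power for the group difference in the follow-up-centred intercept is about 36%, 51% and 98% at d = .2, .25 and .5; 80% power requires d of about .35.*
3. Restrict the claim of adequacy for lower-than-expected effects to the contrasts and range of *d* for which it is shown.
4. If the expected *d* of .5 is a whole-period slope difference, report the 78%.

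The cost is SAP wording and a less favourable stated power for the follow-up test. Sample size, model and tests stay as they are.
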